1. LIST OF ABBREVIATIONS

Abbreviation Definition					
AMG	Arzneimittelgesetz [German Medicinal Products Act]				
mRCC	Metastatic Renal Cell Carcinoma				
GIST	Gastrointestinal stromal tumors				
mTOR	Mammalian Target of Rapamycin				
VEGF	vascular endothelial growth factor				
c-KIT	Stem Cell Factor Receptor				
MCL	Mantle cell lyphoma				
FTL-3	FMS-like tyrosine kinase 3				
RET	Rearranged During Transfection Receptor				
СҮР	Cytochrome P450				
FKSI-15	FACT-Kidney Cancer Symptom Index-15				
EQ-5D	EuroQoL-5D				
RCC	Renal cell carcinoma				
IRB/IEC	Institutional Review Board (IRB)/Independent Ethics Committee (IEC)				
ISPE	International Society for Pharmacoepidemiology				
ICI	Immune Checkpoint Inhibitor				
TKI	Tyrosine Kinase Inhibitor				

[figure not shown]

3. AMENDMENTS AND UPDATES

Amendment Number	Date of Amendment	Substantial Amendment	Reason	
I	09/16/2009	Registry to evaluate the safety, tolerability and efficacy of temsirolimus in the evaluation of patients with advanced renal cell carcinoma and mantle cell lymphoma		
II	10/28/2010	Registry to evaluate the safety, tolerability and efficacy of temsirolimus and sunitinib during the treatment of patients with advanced renal cell carcinoma, mantle cell lymphoma and gastrointestinal stromal tumor (GIST)	Extension to sunitinib	
III	10/20/2012	Registry to evaluate the safety, tolerability and efficacy of temsirolimus, sunitinib and axitinib during the treatment of patients with advanced renal cell carcinoma, mantle cell lymphoma and gastrointestinal stromal tumor (GIST)	Extension to axitinib	
IV	11/26/2015	Registry to evaluate the safety, tolerability and efficacy of temsirolimus, sunitinib and axitinib during the treatment of patients with advanced renal cell carcinoma, mantle cell lymphoma and gastrointestinal stromal tumor (GIST)	12-month recruitment extension	
V	09/12/2016	Registry to evaluate the safety, tolerability and efficacy of temsirolimus, sunitinib and axitinib during the treatment of patients with advanced renal cell carcinoma, mantle cell lymphoma and gastrointestinal stromal tumor (GIST)	24-month recruitment extension	

Amendment Number	Date of Amendment	Substantial Amendment	Reason
VI	10/30/2017	Interim documentation of non-Pfizer substances such as nivolumab or cabozantinib so that e.g. the therapy sequence of sunitinib followed by nivolumab followed by axitinib can be documented. Extension of recruitment phase by 3 years.	Data from routine use of sunitinib followed by novel therapy options, followed by axitinib, to assess the efficacy and tolerability of axitinib in the third or later line in a differentiated manner.
VII	09/28/2020	Discontinuation of question from Amendment VI due to insufficient inclusion of evaluable patients. Reduction of the recruitment period by 12 months	Based on the new approval of ICI in combinations with other ICI or TKI in the first line, the primary use of sunitinib in the therapy sequence shifts to later lines of therapy and as a result, this also applies to the interim documentation and the documentation of axitinib. After evaluation of patient recruitment and inclusion into the various documentation stages, the number of patients calculated to answer the question (Amendment VI) was not reached within the extension period, and the question cannot be answered.

Pfizer - Confidential

4. MILESTONES

Milestone	Planned date			
Start of data collection	January 2008			
End of data collection	12/31/2021			
Final Study Report	11/30/2022			

5. RATIONALE AND BACKGROUND INFORMATION

5.1. Background information

The present registry is a multi-center, prospective, non-interventional investigation according to § 4, Number (23), Clause 3 AMG, which is being conducted according to the joint recommendations of the Federal Institute for Drugs and Medical Devices and the Paul Ehrlich Institute for planning, conducting and analyzing observational research.

Participation in this registry is not meant to lead to a change in routine therapy, i.e. diagnostic and therapeutic practices of the physicians involved will not be affected. Temsirolimus, sunitinib and axitinib are subject to prescription requirements, and are physician prescribed. Study medication will not be provided within the scope of the registry.

The registry will be reported to the German Association of Statutory Health Insurance, the umbrella association of health insurance funds, private health insurance funds, and to the Federal Institute for Drugs and Medical Devices, according to § 67 Paragraph 6 AMG.

This registry was registered based on the VFA recommendations for improving quality and transparency of non-interventional studies (May 2012). (http://www.clinicaltrials.gov).

[figure not shown]
The initial observational plan and the patient information sheet and informed consent form were submitted to the Ethics Committee in Münster for review and received a positive opinion on 11/21/2007. The positive vote for Amendment I took place on 09/16/2009. The positive vote for Amendment II was on 06/17/2010, for Amendment III on 10/08/2012, for Amendment IV on 01/11/2016 and for Amendment V on 09/30/2016. With Amendment VI, an updated version of the patient information sheet and Informed Consent Form for advanced RCC comes into effect. Amendment VII specifies that the recruitment period is to be shortened by 12 months since, due to the new approval of ICI in combinations with other ICI or TKIs in the first line, the primary use of sunitinib in the therapy sequence shifts to subsequent lines of therapy and as a result, this also applies to the interim documentation and the documentation of axitinib. After evaluation of patient recruitment and inclusion into the various documentation stages, the number of patients calculated to answer the question (Amendment VI) was not reached within the extension period, and the question cannot be answered.

Physicians participating in this registry agree to inform patients about the registry and obtain advance written informed consent from the patient. This includes the inclusion of pseudonymized patient data, the use of the data collected, and access to the medical records for review of the data by third parties.

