6. SCIENTIFIC QUESTION AND OBJECTIVE

The treatment of metastatic renal cell carcinoma has undergone substantial changes in a very short time. In recent years, the introduction of various new substances for the treatment of advanced RCC has led to new scientific questions. Temsirolimus and sunitinib are current standard therapies in the first-line therapy of advanced RCC. Temsirolimus is approved for first-line treatment of advanced RCC in adult patients who have at least 3 of 6 prognostic risk factors.

Sunitinib is approved for the treatment of advanced/metastatic RCC. Axitinib has been developed to treat advanced RCC in adult patients after failure of prior therapy with sunitinib or a cytokine.

As of August 2009, temsirolimus is also another therapy option for patients with relapsed and/or refractory mantle cell lymphoma (MCL). In addition, sunitinib is used in patients with unresectable and/or metastatic gastrointestinal stromal tumors (GIST) following imatinib failure or intolerance.

In April 2016, the active substance nivolumab was approved as the first immuno-oncology medicinal product for monotherapy of advanced renal cell carcinoma in adults after previous therapy. In addition, in August 2016, the combination of lenvatinib/everolimus was approved for the treatment of adult patients with advanced RCC after previous treatment with therapy targeted towards the vascular endothelial growth factor (VEGF) and in September 2016, the active substance cabozantinib was approved for therapy of advanced RCC in adults after previous therapy targeting VEGF.

[figure not shown]
Routine use of drugs in routine clinical practice is subject to additional challenges that are generally not fully covered by clinical trials. Therefore, the aim of this registry is to gain an overall picture regarding the efficacy, tolerability, and safety of temsirolimus, sunitinib, or axitinib therapy in patients with advanced renal cell carcinoma, relapsed/refractory mantle cell lymphoma (MCL), and gastrointestinal stromal tumors (GIST) under the conditions of routine use.

In a highly evolving therapeutic setting for advanced RCC, reflected in the current S3 guideline, there is a lack of data from routine use of sunitinib, followed by novel therapy options, followed by axitinib, to assess the efficacy and tolerability of axitinib in the third or later line in a differentiated manner.

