Separate evaluations for third line use of axitinib following prior therapy with sunitinib in the first line followed by e.g. nivolumab, cabozantinib, or lenvatinib/everolimus in the second line are urgently needed. The efficacy of axitinib can continue to be documented after directly preceding therapy with sunitinib. These investigations allow a comparison of the efficacy and tolerability of axitinib in different lines.

Therefore, the following information is of particular interest during the course of the investigation:

- Efficacy (maximum response, survival time, progression-free time)
- Treatment tolerability (assessment by physician)
- Safety profile (overall incidence of adverse events and rate of side effects) of patients with advanced RCC, r/rMCL and GIST receiving treatment with temsirolimus, sunitinib, or axitinib
- Profile, comorbidities and characteristics of patients receiving treatment with temsirolimus, sunitinib, or axitinib
- The sequence of systemic therapies for advanced RCC, MCL, and GIST
- Patient interview on quality of life in advanced RCC patients

Temporal sequence

The following time points were defined as the minimum period for the implementation of the registry:

- Patient Recruitment Phase: January 2008 December 2020
- Recruitment rate: 100 patients/year per product
- Average observation period per patient: 6 months for temsirolimus, 12 months for sunitinib, 6 months for axitinib
- Field Phase: December 2021
- Total duration: 14 years + 1 year evaluation and report (2022)

Since the goal is to keep patients in the registry for life, the registry can be continued indefinitely.

The end of data collection is scheduled for December 2021.

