In total, the treatment of approximately 100 patients per year and product should be documented. This number of patients was chosen to capture a broad range of medical prescription habits and assess the target criteria as significantly as possible. The probability of occurrence of at least one "uncommon" (>1/1000, <1/100) AE is between 0.33 and 0.98 and for a "rare" AE (>1/10,000,<1/1000), between 0.04 and 0.33.

The planned number of 200 sites to be included according to Amendment III allows a representative cross-section across German oncology practices or clinics.

With Amendment VI, the efficacy of axitinib regarding the progression-free survival and overall survival is to be evaluated in the 3rd (and 4th) line of therapy and a correlation with patients on axitinib in the 2nd line of therapy is to be performed.

Patients already documented in STAR-TOR (n = 92; status of 06/30/2017) who received axitinib in the 2nd line of therapy, i.e. with a treatment course of sunitinib-axitinib, will be used as a (historical) comparison group for the comparison with the 3rd and 4th line of therapy, particularly because patients with axitinib in the 2nd therapy line are only rarely expected after the guideline amendments and therefore cannot be newly enrolled.

Patients already documented in STAR-TOR with axitinib in the 3rd line of therapy or 4th line of therapy should not be used to answer the expanded question (see above) as none of these patients received nivolumab or another active substance newly approved in 2016 in the 2nd line of therapy, but received other therapeutic options. It cannot be excluded that the deviating pretreatment/treatment course will impact the efficacy of axitinib in the subsequent lines of therapy as compared with current therapy guidelines.

[figure not shown]
Approximately 45 patients with a PFS event should be documented in the 3rd line with axitinib after the previous therapy sequence, e.g. sunitinib - nivolumab. Therefore, mPFS and mOS can be estimated with sufficient precision (see Statistical Analysis Plan). In order to recruit 45 new third-line axitinib patients after e.g. sunitinib-nivolumab pretreatment in STAR-TOR, approximately 45 months will be required (assuming the usual therapy periods).

Assuming that the last patient is enrolled after 45 months and a progression event (or death) occurs after approximately 6 months, a runtime of approximately 4 years should be assumed after implementation of Amendment VI.

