[figure not shown]
With Amendment VII, the additional documentation period defined in Amendment VI is reduced by one year. As of September 15, 2020, 17 patients were registered in an interim documentation. Of these, 2 patients received follow-up therapy with axitinib. It is shown that the approval of three new ICI combinations which are all prominently represented in guidelines has reduced recruitment for sunitinib patients in first-line therapy (prerequisites for later use of axitinib) and/or has been moved to later lines of therapy. Documentation of 45 patients in the stated time does not seem possible at this recruitment rate to answer the question of Amendment VI. Therefore, the further recruitment phase is reduced by one year (to the end of December 2020).

Discussion of potential bias sources

In this non-interventional registry, the selection of documented patients is not subject to a randomization mechanism, so that a selection bias cannot be excluded.

A comparison of the safety and efficacy of temsirolimus, sunitinib, and axitinib is planned. Potential confounders will be considered and will be included in the statistical analysis plan accordingly. Subgroup analyses, e.g. patients stratified by concomitant diseases, age, and gender, may be performed in addition, if appropriate.

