Adverse events	X	X	X	X	X	X	X	

Efficacy								
Risk prognosis	X				X			
CT / MRT	X	X				X		
Ultrasound	X	X				X		
Chest X-ray	X	X				X		
Tumor assessment		X		X		X		
Physician's assessment of efficacy and tolerability		x				X		
Physician's overall assessment of treatment response			X	Х			X	
PRO: quality of life	X	Х			X	X		

Study population

It is planned to recruit 100 patients per year and treatment over a total recruitment period of 156 months, resulting in approximately 1.600 patients in summary. Patients should only be included after physician's decision to treat the patients with either Torisel®, Sutent® or Inlyta®.

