1.3-1.4	Tumor anamnesis - other information	GIST	SAFETY, EAS	.1 Frequency table for size of primary tumor, sample statistics for number of mitoses, frequency table for primary mutation analysis performed?, frequency table for type of KIT-mutation .2 Frequency table for mutation analysis performed in recidive?, frequency table for type of mutation
CCI				
1.3-3	ECG	mRCC, GIST	SAFETY, EAS	Frequency tables for normal/abnormal ECG by time window

Table No.	Title	Treatment/ Indication	Analysis set	Description
CCI				

Table No.	Title	Treatment/ Indication	Analysis set	Description
CCI				
				, number of transplantations, R0 resection reached

Table No.	Title	Treatment/ Indication	Analysis set	Description
CCI				

Table No.	Title	Treatment/ Indication	Analysis set	Description
CCI				
2	Effectiveness			
2.1	Response to therapy			
2.1-1	Course of response to therapy	All	EAS	Frequency table by time window (in total and by patient risk groups)

Table No.	Title	Treatment/ Indication	Analysis set	Description
2.1-2	Best response	All	EAS	Frequency table for best response in total and confirmed / not-confirmed (the latter not for Torisel® MCL); Frequency table for best response excluding patients "not assessable" only for MCL Listing of reasons for not assessable best response; Frequency table for best response by patient risk groups
2.1-3	Used diagnosis technique	All	EAS	CT, Thorax X-ray, MRT, Ultrasonic testing, PET, Bone scan, Clinical (by time window and for best response)
2.2	Overall survival			
2.2-1	Kaplan-Meier estimates for Overall survival	All	EAS Sequence analysis	Time to 25%, median and 75% survival with confidence intervals incl Kaplan-Meier curve on all patients
2.2-2	Kaplan-Meier estimates for Overall survival by patient risk groups	mRCC	EAS	 .1 Physicians prognosis of patients risk .2 Risk groups according to Motzer score .3 Risk groups according to modified Motzer score .4 Risk groups according to Motzer score for pretreated patients .5 by treatment sequence .6 by treatment and treatment line. .7 1st line patients by risk (poor vs. non-poor) .8 by LDH ≤ 300 U/l vs > 300 U/l incl. Log-ranktest and Kaplan-Meier curves

Table No.	Title	Treatment/ Indication	Analysis set	Description

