2.2-2	Kaplan-Meier estimates for Overall survival by patient risk groups	MCL	EAS	.1 Risk groups according to MIPI score at time of primary diagnosis .2 Risk groups according to current MIPI score .3 2 nd and 3 rd line .4 2 nd to 4 th line .5 4 th line and beyond .6 5 th line and beyond .7 Patients with OR (CR+PR) .8 Patients with (MR + SD) .9 Patients with clinical benefit (CR+PR+MR+SD) .10 Patients ≤ 65 vs. patients > 65 yrs. including Kaplan-Meier curves .1 OS all patients excluding "not assessable" patients .2 OS patients with OR (CR+PR) vs. (MR+SD) vs. PD .3 OS patients with clinical benefit (CR+PR+MR+SD) vs. PD .4 OS Temsirolimus 2 nd to 4 th line (1 − 3 prior therapies) vs. 5 th line and beyond (≥ 4 prior therapies) .5 OS 2 nd to 3 rd line Temsirolimus (1 − 2 prior therapies) vs. 4 th line and beyond (≥ 3 prior therapies)
2.2-2	Kaplan-Meier estimates for Overall survival by patient risk groups	GIST	EAS	.1 Risk groups according to Fletchers risk table .2 Risk groups according to physician's prognosis
2.2-3	Frequency table of patients status by time window (survival phase)	All	EAS	
2.3	Progression free survival			
2.3-1	Kaplan-Meier estimates for Progression free survival	All	EAS Sequence analysis	Time to 25%, median and 75% survival with confidence intervals including Kaplan-Meier curve on all patients

Table No.	Title	Treatment/ Indication	Analysis set	Description
2.3-2	Kaplan-Meier estimates for Progression free survival by patient risk groups	mRCC	EAS	.1 Physicians prognosis of patients risk .2 Risk groups according to Motzer score .3 Risk groups according to modified Motzer score .4 Risk groups according to Motzer score for pretreated patients .5 by treatment sequence .6 1st line patients .7 1st line patients by risk (poor vs. non-poor) .8 2nd line vs. higher lines .9 2nd vs. 3rd line vs. higher lines .10 patients ≤ 65 yrs vs. > 65 yrs .11 by LDH low (≤ 300 U/l) vs high (> 300 U/l) .12 by histology (clear cell vs. other) Kaplan-Meier curves incl Log-Rank-Test .1 PFS 1st line vs. 2nd line and higher .2 PFS 1st line vs. 2nd line vs. 3rd line and higher .3 PFS ≤ 65 yrs vs. > 65 yrs .4 PFS LDH low (≤ 300 U/l) vs high (> 300 U/l) .5 PFS clear cell histology vs. other histology

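### The mRCC comparisons of OS and PFS by line of therapy take no account of enrolment period, although the protocol says the lines in which sunitinib and axitinib are used changed over time

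*Protocol*

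**What the plan says.** **Line of use changed over time.** Protocol section 3 (Amendment VII) and section 5.1 say that, because of newly approved first-line ICI combinations, "the primary use of sunitinib in the therapy sequence shifts to subsequent lines of therapy", and that axitinib documentation follows. Section 11 (case number estimate) says three new combinations "has reduced recruitment for sunitinib patients in first-line therapy" or moved it to later lines. For axitinib, the same section says "patients with axitinib in the 2nd therapy line are only rarely expected after the guideline amendments". It adds that a different pretreatment might affect how well axitinib works, and for that reason keeps earlier third- and fourth-line axitinib patients out of the Amendment VI question.

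**Enrolment window.** Section 6 gives "Patient Recruitment Phase: January 2008 December 2020"; SAP 2.1 plans recruitment "over a total recruitment period of 156 months". Sunitinib joined with Amendment II (28 October 2010) and axitinib with Amendment III (20 October 2012).

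**Analysis.** SAP section 9 repeats tables by treatment and indication. For mRCC, Table 2.2-2 row .6 gives OS "by treatment and treatment line", in a table that includes log-rank tests. Table 2.3-2 includes curves with log-rank tests for "PFS 1st line vs. 2nd line and higher" and for first versus second versus third and higher lines. The strata in SAP 8.2.3 are indication, risk, line, LDH, prior response, age and, for PFS, histology. Enrolment year, period and amendment are absent. Documentation under earlier protocol versions is distinguished only in the disposition counts of Table 1.1-6.1.

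**The concern.** By the protocol's account, first-line sunitinib patients come mostly from earlier years and later-line patients more from recent ones; for axitinib, second-line use becomes rare late in the window. Line and enrolment date therefore move together within each drug. If survival also changed over those years, for instance because more treatments became available afterwards, an unstratified line comparison mixes the two. If survival improved, the mixture flatters later lines and could hide a real disadvantage. One pooled median per drug would also describe neither the earlier nor the later setting.

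Section 11 (bias sources) promises that potential confounders will be carried into the SAP. Calendar time, which the protocol itself describes, is not there.

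**Working it through.** **1. The plan's own window.** January 2008 to December 2020 inclusive is 13 × 12 = 156 months, matching SAP 2.1. This is the registry window. Counting from the month after each amendment:
- Sunitinib, November 2010 to December 2020: 2 + 120 = 122 months.
- Axitinib, November 2012 to December 2020: 2 + 96 = 98 months.

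**2. Where the breaks lie.** The protocol describes two events.
- April 2016: "In April 2016, the active substance nivolumab was approved as the first immuno-oncology medicinal product" (section 6), for use after previous therapy. This changes what follows sunitinib and what precedes axitinib.
- The arrival of first-line ICI combinations, which moved sunitinib itself. The documents give no date. Amendment VI (30 October 2017) still planned around first-line sunitinib, and Amendment VII (28 September 2020) reports the shift as having happened.

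November 2017 to December 2020 is 2 + 36 = 38 months. With even enrolment, at most 38/122 = 31% of sunitinib patients fall after the second event. Since section 11 says first-line sunitinib recruitment fell, the share is probably smaller.

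**3. Size, illustration only.** The documents give no line mix or survival by period, so every input here is assumed: 600 sunitinib patients, two eras, 80% first-line in the early era, early median OS 24 months, exponential survival, censoring uniform over 24-120 months (early) or 12-48 months (late), no true line effect, 1,000 runs per setting.

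One setting by hand: 20% late era, first-line share falling from 80% to 20%, late-versus-early hazard ratio 0.6.
- Later-line patients: early 0.8 × 0.2 = 0.16, late 0.2 × 0.8 = 0.16, so 50% are late-era.
- First-line patients: early 0.8 × 0.8 = 0.64, late 0.2 × 0.2 = 0.04, so 0.04/0.68 = 5.9% are late-era.
- Average initial hazards: 0.5 + 0.5 × 0.6 = 0.80 and 0.941 + 0.059 × 0.6 = 0.976.
- Apparent later-versus-first-line hazard ratio: 0.80/0.976 = 0.82 at the start of follow-up. The simulated value over the whole follow-up is 0.85.

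Simulated later-versus-first-line hazard ratio, unstratified:

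| Late-era share | First-line share, late era | Era HR 0.8 | Era HR 0.6 |
|---|---|---|---|
| 10% | 50% | 0.98 | 0.95 |
| 10% | 20% | 0.96 | 0.91 |
| 20% | 50% | 0.96 | 0.91 |
| 20% | 20% | 0.93 | 0.85 |
| 40% | 50% | 0.94 | 0.87 |
| 40% | 20% | 0.90 | 0.78 |

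With an era hazard ratio of 1.0 the unstratified result is 1.00-1.01: without a change in outcome there is no bias. Stratified by era, the hazard ratio is 1.00-1.01 in every setting. The 40% rows exceed the 31% ceiling from step 2, so 0.78 is an outer bound for sunitinib under these assumptions.

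**The case against.** **Descriptive analysis.** Section 11 calls the evaluation purely descriptive, and SAP 4.1 and 4.2 have no hypotheses or decision rules. SAP 8.1.2 names log-rank tests only for prognosis and risk groups, and the PFS row of SAP 8.2.3 lists none; only the table list attaches them to line for PFS. This stands: no conclusion depends on p < 0.05. A descriptive contrast can still be confounded, and the table list still produces these tests.

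**April 2016 as the single break.** A reader might infer that sunitinib moved to later lines from April 2016, and hence that the line tests would reject far too often. The documents do not support this. That approval was for use after prior therapy, while sections 3 and 5.1 tie the shift to the later first-line combinations. With a late shift and few late patients the bias is close to nil. A single split at April 2016 would also leave the second event mixed within its later stratum.

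**PFS and axitinib.** Drugs given after progression act on OS, not on PFS of the current therapy. That stands for sunitinib. For axitinib, section 11 itself says changed pretreatment may matter, so PFS is relevant there. Late axitinib data may be sparse: of 17 patients in interim documentation by 15 September 2020, 2 went on to axitinib.

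**Other safeguards.** Selection bias is acknowledged, results are also shown by treatment sequence, and interim analyses repeat the same content. None of these separates enrolment periods; interim cuts show earlier patients with shorter follow-up, never the late patients alone.

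**Conclusion.** The gap is real and modest. The protocol links line to calendar time for both drugs, and nothing in the SAP handles calendar time for OS or PFS, so the line contrasts in mRCC can be confounded by enrolment period. Bias requires both a changed line mix and a changed outcome. The documents assert the first, and for axitinib allow that the second is possible; they quantify neither.

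For sunitinib, the illustration runs from a hazard ratio of 0.98 (10% late patients, moderate changes) to about 0.8-0.9 under stronger assumptions. No figure is offered for axitinib. Two stronger readings are not supported: that all mRCC data are pooled from 2008 (2010 and 2012 are the relevant starts for these drugs), and that the line results are known to be wrong.

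**What to change.** Add a sensitivity analysis to SAP 8.1.2 for mRCC, sunitinib and axitinib:

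1. Tabulate line of therapy by enrolment period for each drug. Define period by the baseline visit of that therapy, and state which date is used where a second therapy had no separate starting visit.
2. Repeat Tables 2.2-1 and 2.3-1 by period.
3. Add period-stratified versions of the line log-rank tests (Table 2.2-2 row .6; Table 2.3-2 curves .1 and .2).

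Use three periods: before April 2016, April 2016 to 30 October 2017 (Amendment VI), and after that. A pre-specified finer calendar split would also serve. Treat OS as the main target, with PFS mainly for axitinib. Name calendar time in the discussion of bias, and align SAP 8.1.2 and 8.2.3 with the table list on where log-rank tests by line are done.

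Cost: SAP wording and one variable derived from the baseline date that SAP A1.3 already uses for OS and PFS; no new data. Groups will be smaller and intervals wider within each period, especially the last.
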